### 7.1 Procedures and Study Visits

Patients will attend a total of 3 visits during the study. The description of the activities, procedures and tests to be performed at each visit is detailed below:

## 1. Screening and Start of Run-in period (Visit 1, Week -4):

The following procedures/assessments must be completed during the Screening on the same day prior to the run-in period (Visit 1):

- Obtaining informed consent
- Checking inclusion and exclusion criteria
- Recording of medical history
- Recording of prior and concomitant medications
- Collection of demographic data
- Recording concurrent diseases and medical conditions
- Antihypertensive treatment with NEB or ZOF monotherapy
- Physical and vital signs examination
- BP measurement
- Electrocardiogram (ECG)
- Laboratory tests (see Section 10.2) (A follow-up phone call will be made within 24 hours in case of any abnormality and clinically relevant results from the laboratory tests according to the Investigator)
- Urine pregnancy test
- AEs and serious adverse events (SAEs) assessment

Identification Number: FORM-000050125

Previous Doc Number:
CTWI10A

Version Number: 1.0, CURRENT

#### **Protocol Template**

Sponsor: Menarini Pharmaceutical Study Code: MEIN/19/ZoNe-HYP/001

Protocol Version\_1 of 16/07/2020

The subjects meeting all inclusion criteria and none of the exclusion criteria will enter into the run-in period on the same day and will receive monotherapy of ZOF 30 mg or NEB 5 mg.

- Patients who are already on therapy with ZOF 30 mg or NEB 5 mg will be provided with the same medication
- Patients taking any other BBs will be provided with NEB 5 mg, and patients taking any other ACE-i will be provided with ZOF 30 mg

### 2. Start of the assessment period (Visit 2, Week 0):

At the end of the run-in period (treatment with monotherapies for 4 weeks  $\pm 2$  days), only the patients with uncontrolled BP (SBP/DBP >130/80 mmHg), who tolerated the treatment and whose adherence to the therapy ranges from 80% to 120%, will enter the assessment period.

The starting of extemporaneous combination ZOF 30 mg /NEB 5mg dosing is noted as Week 0.

The following procedures/assessments must be completed:

- Recording of concurrent diseases and medical conditions
- Study drug dispensing (Patients will be provided with the extemporaneous combination ZOF 30 mg/NEB 5 mg)
- Recording of concomitant medications
- Physical examination and vital signs
- BP measurement
- ECG
- Urine pregnancy test (UPT)
- Compliance assessment by return of ZOF and NEB tablets (also empty blisters) and accountability
- AEs and serious adverse events (SAEs) assessment

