#### 7. STUDY DESIGN

This is a phase IV, open-label, multicenter, multinational, interventional study to assess the effectiveness and safety of the extemporaneous combination of NEB and ZOF in grade 1 to 2 hypertensive patients versus each monotherapy (NEB or ZOF).

The study will be conducted in approximately 15 sites in the European Union countries. The total study duration is 12 weeks including a run-in period of 4 weeks and an assessment period of 8 weeks.

At Visit 1, after providing informed consent, the eligible grade 1-2 hypertensive patients (with blood pressure [BP] ranging from ≥140/90 mmHg to ≤179/109 mmHg), who were on treatment since at least 1 month, with any ACE-i or BB including ZOF 30 mg and NEB 5 mg will be screened for the eligibility criteria including BP. On the same day, the eligible patients will enter the run-in period of 4 weeks (Week -4 to Week 0). Efforts will be made to achieve 1:1 ratio in the enrolment of patients receiving any ACE-i or BB. The eligibility for grade 1-2 hypertension will be based upon the European Society of Cardiology/European Society of Hypertension (ESC/ESH) guidelines 2018, and the BP criteria is defined as mean sitting SBP ≥140 mmHg and ≤179 mmHg and/or mean sitting DBP ≥90 mmHg and ≤109 mmHg.

During the run-in period of 4 weeks (Week -4 to Week 0):

 Patients on ZOF 30 mg or NEB 5 mg will continue the same therapy. Patients on any other ACE-i will be assigned to monotherapy with ZOF 30 mg and the patients on any other BB will be assigned to monotherapy with NEB 5 mg, respectively.

Patients with controlled BP (sitting SBP/DBP ≤130/80 mmHg), at Week 0 (Visit 2), patients with uncontrolled BP (sitting SBP/DBP >130/80 mmHg) whose adherence to the treatment is not included from 80% to 120% or patients who cannot tolerate one of the monotherapies will not proceed further into the study.

Identification Number: FORM-000050125

Previous Doc Number:
CTWI10A

Version Number: 1.0, CURRENT

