#### **Protocol Template**

Sponsor: Menarini Pharmaceutical Study Code: MEIN/19/ZoNe-HYP/001

Protocol Version 1 of 16/07/2020

After the run-in period, the patients will be treated with the extemporaneous combination of NEB 5 mg and ZOF 30 mg for 8 weeks (assessment period), ie, from Week 0 (Visit 2) till Week 8 (Visit 3).

To correctly evaluate the additional effect of the combination therapy, the number of patients with uncontrolled BP on NEB or ZOF monotherapy needs to be balanced at Visit 2. In order to maintain a 1:1 ratio during the assessment period, a cap of 110 patients for each arm (ie, NEB and ZOF) will be included at Visit 2 in order to maintain a balanced number of uncontrolled patients entering the assessment period for each drug. The evaluation will be done every 50 patients. If the rate of entrance in the assessment period for one of the 2 tested drugs will deviate more than 5%, a corrective measure will be initiated: according to the enrolment site statistics, one or more sites will be informed to enrol a greater number of patients being treated with the least represented drug in the assessment period. A total number of 290 patients will be screened considering 25% of drop-out rate, to obtain approximately 216 completed patients at the end of the study.

Blood pressure and heart rate will be measured at all visits using a calibrated, fully automated machine with a cuff that is appropriate to the size of the upper arm. If a fully automated machine is not available, BP may be measured manually. The same method (either automated or manual) and the same arm (right or left) must be used throughout the study. The patient should be in a seated position with feet touching the floor. Patients should be seated quietly for several minutes in a chair with their backs supported, their feet flat on the ground, and their arms bared and supported at heart level. At each clinic visit, 3 BP measurements will be collected 24 hours (±3 hours) after the last study drug intake and the mean values will be recorded. Each BP measure must be recorded within ±2 mmHg. Patients will be instructed to take study medication at the same time each day except on the days of study visits when study medication will be taken after all visit evaluations have been performed.

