#### BP measurements:

Blood pressure will be measured at all visits. The arm with the higher mean DBP will be identified at Screening and will be used in all subsequent visits for BP monitoring. Blood pressure measurements should be performed as nearly as possible at the same time of the day (between 7:00 AM to 12:00 noon), on the same arm, by the same personnel, and using the same calibrated equipment at each visit.

All BP measurements will be performed after at least 10 minutes of rest; in sitting position in triplicate (spaced by at least 1 minute), and once in standing position using a calibrated and validated automated sphygmomanometer. The mean of the 3 recordings in the sitting position will be used as the BP value for that visit and recorded in the source document and in the eCRF. All BP measurements during the treatment period will be performed as through readings (ie, 24+3 hours after the last study treatment intake). For this purpose, patients will be instructed to take study treatment at the same time each day except on the days of study visits when study treatment will be taken after all visit evaluations have been performed.

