#### **6.2.** BASELINE

Unless otherwise specified, baseline is defined as the last non-missing measurement taken same day or prior to reference start date (including unscheduled assessments) before first dose of study medication (combination therapy). Adverse Events (AEs) and medications commencing on the reference start date/time will be considered post-baseline, unless the start time of the AE is known to be prior to the first dosing of the study drug. Since there is no Lab assessment in Visit 2, Lab values collected at Visit 1 will be considered baseline for Lab data.

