### 16. EFFICACY OUTCOMES

#### 16.1. PRIMARY EFFICACY

#### 16.1.1. PRIMARY EFFICACY VARIABLE & DERIVATION

The primary efficacy variable is Change in mean sitting DBP between Week 0 (Visit 2) and Week 8 (Visit 3).

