#### 16.1.3. PRIMARY ANALYSIS OF PRIMARY EFFICACY VARIABLE

The primary objective of this study is to test the hypothesis that

- H0: There is no change in the sitting DBP prior or post combination therapy
- H1: There is a difference in the sitting DBP prior or post combination therapy.

The primary efficacy analysis will be performed for the ITT population. The above hypothesis will be tested as following-

• Change from baseline in sitting DBP from prior and post combination therapy will be compared using paired t-test. The p-value will be presented using paired t-test.

Document: \\ieedc-vnasc01\BIOSdata\Menarini\NebZof\KZA41200\Biostatistics\Documentation\SAP

Author: [name] Version Number: Final V1.0

Version Date: [14Dec2021]

Template No.: CS\_TP\_BS016 Revision 6 Reference: CS\_WI\_BS005

Page 26 of 37

- The primary endpoint will be presented in a descriptive manner using n, mean, median, SD, Q1, Q3, minimum and maximum.
- Assumption of normality will be investigated using Wilk-Shapiro test. If violation is observed, then paired ttest will be replaced by Wilcoxon signed rank test.

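### The Visit 2 blood pressure both admits the patient and serves as baseline, so regression to the mean from the entry rule counts as combination effect in an uncontrolled test against zero change

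*Protocol*

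**What the plan says.** - **Entry.** After four weeks of monotherapy, Protocol 7.1 (Visit 2) admits "only the patients with uncontrolled BP (SBP/DBP >130/80 mmHg), who tolerated the treatment" and whose adherence was 80% to 120%. Protocol 7 removes patients found controlled at that visit.
- **The value used.** Protocol 10.1: "The mean of the 3 recordings in the sitting position will be used as the BP value for that visit".
- **Baseline.** SAP 6.2: "baseline is defined as the last non-missing measurement taken same day or prior to reference start date", before the first combination dose. In practice this is the Visit 2 value. It starts the primary DBP change (SAP 16.1.1) and the secondary SBP change (SAP 16.2.1).
- **Control.** None. Protocol 14.1 states that no randomization is required, and every patient in the assessment period gets the combination.
- **Test.** SAP 16.1.3: "H0: There is no change in the sitting DBP prior or post combination therapy". A paired t-test is used, two-sided under SAP 6.5, with no covariate adjustment (SAP 7.1). The only sensitivity analysis uses the PP set (SAP 16.1.4), which is drawn from patients who passed the same entry rule.
- **Claim.** Protocol 7 justifies balancing the two monotherapies with "To correctly evaluate the additional effect of the combination therapy", and the stated aim is a comparison with each monotherapy.
- **Sample size.** Protocol 14.2 uses a 4 mmHg change, SD 10 and a null value of 2 mmHg.

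SAP 3.3 recognises that the entry rule forces the goal rate at Visit 2 to zero, but draws no consequence for the DBP or SBP change. Neither document mentions regression to the mean.

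**The concern.** A patient whose Visit 2 value is high by chance stays in the study, and one whose value is low by chance leaves. Among those who stay, the Visit 2 value overstates usual pressure on monotherapy, so the Visit 3 mean tends to be lower even if the second drug adds nothing. No control group shows the same drift, and a null of zero leaves no allowance for it. The estimated added effect is too large by the amount of the drift, and the p-value can be small without a drug effect. SBP is affected in the same way.

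**Working it through.** **1. The plan's own figure.** One-sample test, δ = 4 − 2 = 2, SD 10, n = ((z₁₋α + z₀.₉₀) × SD/δ)².
- One-sided 5%: ((1.645 + 1.282) × 10/2)² gives 215. With the t distribution it is 216, and power at 216 is 90.1%. The stated 216 reproduces.
- Two-sided 5% against 2 mmHg: 263 (t: 265). Power at 216 is 83.3%.
- Two-sided 5% against 0, δ = 4: 66 (t: 68).
- Attrition: 216/0.75 = 288, stated as 290.

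So 216 matches a one-sided test against 2 mmHg, while the SAP tests zero, two-sided.

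**2. Direction.** With no drug effect, let Visit 2 = T + e₂ and Visit 3 = T + e₃, where T is usual DBP and e₂, e₃ are independent visit errors. Then E(Visit 2 − Visit 3 | entered) = E(e₂ | entered). Entry is likelier when e₂ is high, so this is positive: the bias is always a fall.

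**3. Effect of a given drift on the test** (n = 216, SD 10, standard error 10/√216 = 0.68 mmHg). The two-sided test against 0 is significant from 1.971 × 0.680 = 1.34 mmHg. A one-sided 5% test against 2 mmHg would need 2 + 1.652 × 0.680 = 3.12 mmHg.

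| Drift, no drug effect | Rejects 0 (two-sided) | Rejects 2 mmHg (one-sided 5%) |
|---|---|---|
| 0.5 mmHg | 11% | <0.1% |
| 1.0 mmHg | 31% | 0.1% |
| 1.5 mmHg | 59% | 0.9% |
| 2.0 mmHg | 83% | 5.0% |

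**4. Size of the drift.** The documents give only the SD of change, 10; a visit SD of 10/√2 = 7.07 would produce it. Everything else here is assumed: true BP 148/92, between-patient SD 11/7, visit-to-visit SD 8 to 10 (SBP) and 5 to 7.07 (DBP), SBP–DBP correlation 0.5 between and 0.6 within patients, run-in fall 0/0 to 10/7 mmHg, independent visit errors. Bivariate-normal BP was simulated with the Visit 1 and Visit 2 rules applied and zero combination effect. Rejection is at n = 216 against 0, using each scenario's own SD of change, so it differs slightly from the table above.

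| Meaning of >130/80 | Spurious DBP fall | Rejection |
|---|---|---|
| Either component raised | 0.1 to 1.0 mmHg | 5% to 34% |
| Both raised, at least 75% pass Visit 2 | 0.5 to 1.9 mmHg | about 20% to 84% |
| Both raised, no restriction | 0.5 to 2.9 mmHg | 19% to 99% |

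The 75% restriction reflects the planned 25% total loss. Every case above about 2 mmHg had only about 61% to 65% passing Visit 2.

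A wider set of assumptions (mean DBP 80 to 90, SBP 132 to 145, between-patient SD 6 to 8 and 10 to 12, DBP run-in fall 0 or 5) gives about 0.1 to 1.7 mmHg and 5% to 77% across both readings where at least 75% pass.

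**5. Can it be corrected from planned data?** Fit Week 8 DBP = a + b₁ × (Visit 2 DBP) + b₂ × (Visit 2 SBP) in entrants. Evaluate the fit at the mean Visit 2 values of all adherent, tolerant run-in completers and subtract their mean Visit 2 DBP. In every null scenario of the first set the result was within 0.05 mmHg of zero. With a true 4 mmHg fall it returned 3.99, against a raw change of 5.37.

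**The case against.** **The larger figures need an unlikely reading.** Protocol 7 writes its screening range in the same slash form and defines it as SBP and/or DBP. The split into controlled and uncontrolled patients covers everyone only if one raised component is enough; otherwise a patient at 135/78 has no disposition. This stands, although the text never says so outright. A reader might infer that a spurious fall near 3 mmHg, with near-certain rejection, is to be expected. The documents do not support that: it needs both components raised and a Visit 2 pass rate at odds with the planned 25% loss.

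**The 2 mmHg null already covers it.** For the test it largely would: drift up to 2 mmHg would keep a one-sided 5% test at or below 5%. But that value appears only in the synopsis and Protocol 14.2, and both analysis sections test zero change. It would not correct the estimate either.

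**The measurement is careful.** The value is a mean of three readings after rest, and the run-in separates baseline from the Visit 1 selection. Both help. Triplicates do not remove visit-to-visit variation, however, and Visit 2 selects again on the baseline itself.

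**The correction is imperfect.** With visit errors correlated at 0.3 to 0.5, it left 0.2 to 0.35 mmHg of spurious fall. It also averages over controlled patients who never receive the combination: with an effect that rises with BP (assumed slope 0.3) it gave 3.3 against a true 3.9 in entrants. These points limit it to a supportive role.

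**Conclusion.** The concern holds as a limitation of the design that the plan does not address. One visit's value is both entry criterion and baseline, without a control, in a test against zero. The direction is certain under independent visit errors; the size is not. On the likelier reading and the first set of assumptions it is 0.1 to 1.0 mmHg, at most a quarter of the planned 4 mmHg (1.0/4), and at the low end there is practically no inflation of the 5% level. If both components must be raised, with at least 75% passing Visit 2, it is 0.5 to 1.9 mmHg, up to 1.9/4, or just under half. These ranges rest on assumed means, SDs and correlations.

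A reader might go further and conclude that a significant result would be wholly an artefact. The figures do not show that: a fall of about 4 mmHg would exceed every spurious fall in these ranges. Nor does the point justify replacing the primary success rule. What the plan lacks is any means of telling a small bias from a material one.

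**What to change.** 1. **Supportive estimate.** Add to SAP 16.1.4, and to 16.2.3 for SBP, a regression of Week 8 BP on Visit 2 DBP and SBP in ITT. Evaluate it at the mean Visit 2 DBP and SBP of all adherent, tolerant run-in completers in ENR, including those found controlled. Report the resulting change with a bootstrap 95% CI beside the raw change.
2. **Null hypothesis.** Reconcile the zero-change null in Protocol 14.5.2 and SAP 16.1.3 with the 2 mmHg null in the synopsis and Protocol 14.2, and state the sidedness. Only testing against 2 mmHg would protect the test from the drift.
3. **Wording.** Describe the Visit 2 to Visit 3 change as uncontrolled.

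Do not make the corrected CI the success criterion. Do not treat the Visit 1 to Visit 2 change as a clean benchmark either: it follows selection at Visit 1 and showed 0.6 to 0.9 mmHg of regression with no true change.

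**Cost.** Items 1 and 3 need SAP wording and one extra model per endpoint, with no new data or patients. Item 2 may cost more. Under Protocol 14.7 a change to the primary analysis requires a substantial amendment, and a two-sided test against 2 mmHg has 83.3% power at 216. The supportive estimate assumes a linear relation extended slightly below the threshold and independent visit errors. It refers to all run-in completers and not only entrants, and its CI is wider. It removes only the regression caused by the entry rule, not time, placebo or lifestyle-counselling effects.

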# 3. End of the Assessment Period (Visit 3, Week 8):

The end of assessment period will be considered as end of 8 week ±3 days treatment with the extemporaneous combination ZOF 30 mg/NEB 5mg.

Identification Number: FORM-000050125

Previous Doc Number:
CTWI10A

Version Number: 1.0, CURRENT

#### **Protocol Template**

Sponsor: Menarini Pharmaceutical Study Code: MEIN/19/ZoNe-HYP/001

Protocol Version\_1 of 16/07/2020

The following procedures/assessments must be completed:

- Recording of concurrent diseases and medical conditions
- Recording of concomitant medications
- Physical examination and vital signs
- BP measurement
- ECG
- Laboratory test (A follow-up phone call after will be performed within 24 hours from results in case of any abnormality and clinically relevant results from the laboratory tests according to the Investigator)
- Urine pregnancy test (UPT)
- Compliance assessment by study drug (extemporaneous combination of ZOF 30 mg and NEB 5 mg) return (also empty blisters) and accountability
- AE and SAE assessment
- In case of any patients having an ongoing AE or SAE at the end of the treatment, there
  will be a follow-up telephone call after 2 weeks to ensure patient safety

Note: Patients will be counselled to follow a heart healthy diet as per local or regional guidelines and should be encouraged (as able) to participate in a regular exercise programme throughout the study.

#### 8. SELECTION OF PATIENTS

## **Informed Consent Process**

Prior to the patient's enrolment into the study and before performing any study related procedures, the Investigator or his/her authorized delegate, shall obtain the patient's written, dated, and signed informed consent to participate into the study and to the confidential disclosure, processing and transferring of necessary documentation of the patient's health and personal data to the contract research organization (CRO), Sponsor, and its Affiliates, the competent health authorities (HA), and any other institutions, as legally required and in

Identification Number: FORM-000050125

Previous Doc Number:
CTWI10A

Version Number: 1.0, CURRENT

#### **Protocol Template**

Sponsor: Menarini Pharmaceutical Study Code: MEIN/19/ZoNe-HYP/001

Protocol Version\_1 of 16/07/2020

accordance with the local applicable privacy laws (for the privacy information to be reported on the informed consent form [ICF] refer to Section 19).

The institution and Investigator undertake to duly inform patients about personal data processing and the relevant applicable privacy rights before their participation into the study.

After being duly informed and interviewed by the Investigator, the patient has to freely date and sign the ICF before being enrolled into the study and before undergoing any study procedure. The Investigator must store the original of the signed ICF in the Investigator's File, and the patient will be provided with a copy of it. If a protocol amendment affects the terms of the ICF, it will be revised to reflect the protocol change and submitted to Ethics Committee (EC) and the HA for approval. The Investigator will ensure that this new consent form is signed by all patients subsequently entered in the study and those currently in the study, if affected by the amendment.

#### 8.1 Inclusion and Exclusion Criteria

A patient will be considered eligible to be enrolled in the study only if he/she meets all of the inclusion criteria and none of the exclusion criteria.

#### 8.1.1. Inclusion Criteria

- Male or female Caucasian uncontrolled hypertensive patients ≥18 and <65 years of age (see definition in criterion 3), in monotherapy either with ACE-i or BBs since at least 1 month, at Screening
- 2. Patients are able to understand and have freely given written informed consent at Screening
- Patients with mean sitting SBP ≥140 mmHg and ≤179 mmHg and/or mean sitting DBP
   ≥ 90 mmHg and ≤109 mmHg at Screening
- 4. Patients who are able to comply with all study procedures and who are available for the duration of the study
- 5. Ability to take oral medication and willing to adhere to the drug regimen
- 6. A female patient of childbearing potential is eligible to participate if she is not pregnant, or not breastfeeding. A woman is considered fertile following menarche and until becoming postmenopausal unless permanently sterile. Women of childbearing potential

Identification Number: FORM-000050125

Previous Doc Number:
CTWI10A

Version Number: 1.0, CURRENT

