### 7.5. EXAMINATION OF SUBGROUPS

Subgroup analyses will be conducted as stated in the exploratory analysis sections. It should be noted that the study was not designed to detect treatment differences with high statistical power within subgroups.

The following subgroups will be assessed and described within the exploratory analysis sections on ITT and PP populations.

- Country/Site
- Age (<40 years and  $\ge40$  years)
- Gender (Male, Female, Other)
- Hypertension grade at screening (grade 1 and grade 2)
- Presence of diabetes (patients with or without diabetes)
- Presence of hypercholesterolemia (patients with or without hypercholesterolemia)
- Screening therapy (ACE-i, Beta blocker)
- Run-in period therapy (Monotherapies of ZOF 30 mg or NEB 5 mg)

Hypertension grade at screening is derived as follows;

- Grade  $1 140 \le SBP \le 160$  or  $90 \le DBP \le 100$
- Grade  $2 160 \le SBP \le 180$  or  $100 \le DBP \le 110$

Patients with presence of diabetes and hypercholesterolemia will be identified from the medical history data using the preferred terms. Presence of diabetes can be identified with the preferred terms "Diabetes mellitus" Or "Type 2 diabetes mellitus" and hypercholesterolemia with "Dyslipidaemia" or "Hypercholesterolaemia" or "Hyperlipidaemia". Patients under ACE-i and beta blocker can be identified from the concomitant medication data with anatomical therapeutic chemical (ATC) class "Ace inhibitors, plain" and "Beta blocking agents, selective" respectively.

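### As printed, inclusion criterion 3 admits patients above 179 or 109 mmHg in one component, and the SAP's hypertension grades overlap and stop at grade 2

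*Protocol*

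**What the plan says.** Criterion 3 in Protocol Section 8.1.1, repeated in the Section 2 synopsis, accepts "Patients with mean sitting SBP ≥140 mmHg and ≤179 mmHg and/or mean sitting DBP" "≥ 90 mmHg and ≤109 mmHg at Screening". Section 7 gives the same rule as the definition of the blood pressure criterion: "mean sitting SBP ≥140 mmHg and ≤179 mmHg and/or mean sitting DBP ≥90 mmHg and ≤109 mmHg".

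The same Section 7 describes the population as "the eligible grade 1-2 hypertensive patients (with blood pressure [BP] ranging from ≥140/90 mmHg to ≤179/109 mmHg". The synopsis and SAP Section 3.1 give the same range. Section 8.1 makes eligibility turn on the listed inclusion and exclusion criteria, and none of the 17 exclusion criteria in Section 8.1.2 sets an upper blood pressure limit.

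SAP Section 7.5 lists the subgroup "Hypertension grade at screening (grade 1 and grade 2" and derives it as follows: grade 1 is SBP 140 to 160 or DBP 90 to 100, and grade 2 is SBP 160 to 180 or DBP 100 to 110. There is no third category and no rule for a patient who meets both. SAP Sections 16.3.1 and 16.3.2 use the subgroups to report the number and percentage at blood pressure goal at Visits 2 and 3.

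**The concern.** A closed range joined to another by *and/or* makes all four limits optional, not only the two lower ones. The usual reason for such a connector is to admit patients with only systolic or only diastolic elevation. That requires the lower limits to be alternatives. It does not require the upper limits to be.

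Two things are at stake. First, sites may apply the criterion differently: one follows the printed rule and another follows the described range. Second, the grade variable cannot be programmed from SAP Section 7.5 as it stands. Code that tests grade 1 first, code that tests grade 2 first, and code that sets two independent flags will put the same patient in different groups. With independent flags, the subgroup denominators add up to more than the number of patients. Hypertension grade appears in a stated exploratory objective, so its derivation should have one answer.

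**Working it through.** The documents state no figure to reproduce here; the check is one of logic.

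**Inputs.** Criterion 3 and the 179/109 range come from Protocol Sections 7 and 8.1.1, and the grade rules from SAP Section 7.5.

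**Rules as coded.**
- Criterion 3 as printed: (140 ≤ SBP ≤ 179) or (90 ≤ DBP ≤ 109).
- Described range with the ceiling on both components: (SBP ≥ 140 or DBP ≥ 90), and SBP ≤ 179, and DBP ≤ 109.
- Grade 1: SBP from 140 to 160, or DBP from 90 to 100, limits included. Grade 2: SBP from 160 to 180, or DBP from 100 to 110, limits included.
- The grade rules were also run with strict upper bounds (below 160/100 and below 180/110), in case the reading of the PDF altered the symbols.

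**Individual readings.**

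| SBP/DBP | Criterion 3 as printed | Within 179/109 on both | Grade, bounds as printed | Grade, strict upper bounds |
|---|---|---|---|---|
| 185/95 | admitted | no | 1 | 1 |
| 150/115 | admitted | no | 1 | 1 |
| 185/105 | admitted | no | 2 | 2 |
| 170/115 | admitted | no | 2 | 2 |
| 180/95 | admitted | no | 1 and 2 | 1 |
| 150/110 | admitted | no | 1 and 2 | 1 |
| 185/100 | admitted | no | 1 and 2 | 2 |
| 185/85 | refused | no | none | none |
| 185/115 | refused | no | none | none |
| 170/95 | admitted | yes | 1 and 2 | 1 and 2 |
| 150/105 | admitted | yes | 1 and 2 | 1 and 2 |

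The printed rule refuses 185/85 but admits 185/95, which has the same SBP and a higher DBP. The described range gives no basis for that distinction.

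**All combinations.** The grid is an assumption: whole mmHg, SBP 110 to 220, DBP 60 to 130, pulse pressure at least 20.

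- Admitted above the ceiling: 1605 combinations. With bounds as printed, 745 are grade 1 only (745/1605 = 46%), 768 grade 2 only (48%) and 92 both (6%). With strict upper bounds, 775 are grade 1 (48%) and 830 grade 2 (52%). Each one receives a grade of 1 or 2.
- Inside the ceiling on both components: 1055 + 876 + 479 = 2410 combinations. With bounds as printed, 479 meet both grades (479/2410 = 20%). With strict upper bounds the split is 1055, 955 and 400, so 400/2410 = 17% still meet both. Tightening the boundary symbols alone therefore does not cure the overlap.
- Applying the ceiling to both components loses no in-range combination that criterion 3 now admits, and criterion 3 misses none that the ceiling rule would admit. It leaves the grade overlap untouched.

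These are counts of blood pressure combinations, not expected shares of patients.

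**The case against.** The strongest defence is that the intent is plain. Section 7 names a grade 1-2 population with a ceiling and then offers the *and/or* rule as its definition, so an investigator who enrolled 150/115 would be going against the surrounding text. This stands as evidence of intent, and the problem may well be one connector drafted loosely. It does not settle the matter, because the listed criteria decide eligibility and Section 7 repeats the loose connector as the definition.

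A second defence is that SAP Section 5.4 already removes patients who fail an eligibility criterion from the per-protocol set. A patient at 185/95 meets criterion 3 as printed, so that check would not flag the case unless the data review chose to read the ceiling into it.

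Some stronger readings are tempting but not supported:

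- A reader might infer that every above-ceiling patient is labelled grade 1. The in-range component decides the grade: 185/105 and 170/115 are grade 2.
- A reader might infer that the primary result is compromised. The primary test compares Visit 2 with Visit 3 and does not use the grade. Regression to the mean from an extreme screening value bears mainly on the comparisons from Visit 1, which are exploratory.
- A reader might want a count of affected patients. Any percentage would rest on an assumed distribution, and multiplying it by 290 would be wrong in any case: 290 is the number to be screened, and Section 14.2 places screen failures within its 25% allowance.
- A reader might argue harm from a monotherapy run-in with rescue medication listed as not applicable (Section 9.7). Section 12 lets the investigator stop treatment or withdraw a patient in the patient's interest, so the documents do not show an unprotected group.

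It is also fair to say that SAP Section 7.5 itself disclaims high power within subgroups, and that the planned grade output is counts and percentages.

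**Conclusion.** The point holds as an inconsistency between the operative eligibility criterion and the described population, together with a grade derivation that is not mutually exclusive. The grading fault is the more direct of the two, because it arises for patients fully inside the intended range and persists under either reading of the boundary symbols.

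Its reach is limited to entry into the run-in and to the exploratory hypertension-grade subgroup. Its size in patients cannot be stated from these documents. It should be corrected, but it does not threaten the primary analysis.

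The conclusion rests on the Protocol and SAP text alone. SAP Section 1 cites a protocol addendum of 29 October 2020 that is not among the documents. If that addendum reworded criterion 3, the eligibility half would need to be read again. The grading half would remain, since it is in the SAP that postdates the addendum.

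**What to change.** **Protocol.** Reconcile criterion 3 in Sections 2, 7 and 8.1.1 with the stated 179/109 range, making explicit whether both upper limits apply when only one component is in range. Which rule is intended is for the sponsor to say. The cost is a clarification of wording, handled under the amendment procedure in Section 14.6.

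**SAP Section 7.5.** Assign grade by the higher of the two component grades, with bounds that do not overlap, so that 170/95 and 150/105 each fall in one group. List any screening value above 179 or 109 separately instead of labelling it grade 1 or 2. Whether such a value is an eligibility deviation, and so matters for the per-protocol set, follows from the reconciled criterion and should not be decided in the derivation. The cost is one derivation and one listing, both feasible before database lock with no new data.
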